Due to the problem of attrition in the control group, it has been suggested in the last International Myopia Conference that controlled field studies be performed by a virtual group, without performing a non-inferiority study, since atropine 0.01% could not be taken as gold standard because it is not yet approved and as we said, it is off-label in Argentina. Data on progression in Asia or Europe could be used for this virtual control group, but it would be more convenient to have a virtual control group in one's own living environment. In the case of our country there is already a possible control group of 114 children of 12 years of age on average who were followed up with cycloplegia during the years pre-pandemic and from which it is known that the progression was from 0.43+/-0.52 diopters in one year.³⁶

It is thus proposed to perform a prospective clinical study in 100 children who will be enrolled when in the usual consultation for their eyeglasses control they can choose to do the treatment accessible in our environment (the diluted atropine drop) or a treatment that is possibly equally effective with special glasses designed in our environment. It is

expected that there will be similarity of effect on progression because the lens is based on the principles of defocusing of eyeglasses and contact lenses already proven by the international industry.³⁷ Our lens has the characteristic of being much simpler in its carving and construction, making it more economical for our environment where it has already been presented from the theoretical point of view.³⁸

Moreover, the special myopia control spectacle lacks the possible toxic effects of a drop instilled in the eye for many years until emerging adulthood. In addition, to avoid including children who may have rapid progressions to high myopia, treatment will be offered only to children over 8 years of age. In our environment, where children are outdoors a lot, the progression is slower than in Asian countries and is around -0.50 diopters per year, as we said.³⁶ A strong myopia is the one that exceeds -5.00 diopters.³⁹ Thus the risk for a child included in this project is to progress -0.25 diopters in six months (the resolution limit of the measurement method), so each child who does not respond well with arrest of progression at six months may be removed from the protocol and switched to atropine treatment.

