Given the above-mentioned background, the following study has been designed to evaluate the arrest of myopia progression with the daily use of nationally designed glasses, comparing such progression with a virtual control group of similar age in a population of myopic children and adolescents of the same environment in our country.

WORKING HYPOTHESIS

The nationally designed lenses can be as effective as the proven international industry designs that have been subjected to controlled trials against natural history of the disease.

PURPOSE

To treat a group of consecutive volunteer patients who choose between the affordable treatment in our environment (daily diluted atropine drops for several years) or the special lenses for myopia control designed by the National Industry. The purpose is to compare the progression during one year with the national lenses with respect to the progression with the foreign lenses and/or with the natural history of a virtual control group.

OBJECTIVES

Primary

To assess whether the intervention with locally designed spectacles is well tolerated and adhered to with daily use in childhood and adolescence.

Secondarily

To assess whether intervention with locally designed glasses can control myopia progression in childhood and adolescence.

DEFOCUS GLASSES OF NATIONAL DESIGN

The design of the national defocus lens is based on the original design presented by Carly Lam,⁴⁰ with a 9 mm central zone for distance correction and a correction ring with a +3.50 dioptre defocus between 9 and 32 mm in diameter to act in principle on the para foveal zone which is the one that detects the defocus that governs the growth of the eye.⁴¹ Instead of peripheral defocusing micro lenses that do not alter the visual field in the area of the 32

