ophthalmology offices that are members of the research team. The opticians and ophthalmologists will be asked to watch a video on myopia control developed by the principal investigators where this treatment methodology is explained during the evaluation process at the center of care. The opticians will verify the optical centration in the frames chosen ad hoc, with a modern digital centration system provided by the sponsors. After 15 days, when the glasses with the correct centering are ready, the subjects will go to the optician's office to try on the glasses in that room. On this occasion, as always in these cases, the optician will evaluate the subject's adaptation and mobility in the optician's shop, instructing the child to wear the glasses at home for a couple of days and then to wear them for as long as possible.

SAMPLE AND SAMPLE SIZE

The sample size will be 50 subjects of both genders to compare with the studies abroad that consist of an n between 40 and 90 subjects and the natural history in our country that counted 114 subjects. There will be a group of subjects who will be treated with the nationally designed defocus glasses. Statistical calculation for a difference of 0.25 diopters in progression with respect to controls, for a standard deviation of 0.50 diopters gives an $n = 31$ subjects and taking into account a 20% loss to follow-up the n should equal 38 subjects in the group. Thus reaching 50 subjects exceeds expectations.

METHODS

This field study to test tolerance and percentage of effectiveness of defocus lenses in the control of myopia will include boys and girls from 8 to 15 years of age who voluntarily

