agree to take the test for one year, with no ocular pathology other than myopia, with spherical equivalent (sphere + 50% of the cylinder) between -0.50 D and -5.00 D, with astigmatism less than -2.00 D in each eye, with anisometropia less than -1.00 D, with keratometry less than 47.00 D in the most curved meridian. Genetic syndromes will not be included or ruled out. A complete ophthalmologic evaluation will be performed including tonometry, fundus, subjective refraction and refraction under cycloplegia with two drops of 1% cyclopentolate instilled 5' apart and performed 40' after the last drop. Visual acuities of the subjective refraction will be greater than 8/10 in each eye. Axillary length measurements with optical biometry will be performed at the beginning of treatment at follow-up and at the end of the study. New cycloplegic refractions will be performed during follow-up and at one year of treatment. A survey of habits and history, including reading, outdoors, ON-OFF contrast use, hours of schooling, age of onset of spectacle use and family history of high myopia (also likely use of devices to monitor these habits in selected group) will be conducted. A pair of spectacles and their frames will be provided free of charge to all children studied for one year with the special addendum of peripheral defocus treatment or laser treatment for contrast reduction depending on the treated group. The children will be instructed to wear the glasses especially in front of smartphones, tablets, PC's or books at home after five o'clock in the afternoon and until going to bed, every day of the week including Saturdays and Sundays. During the rest of the day they will use their usual correction without properly updated defocus. As defocus in experimental animals has more effect in stopping experimental myopia in the afternoon than in the morning,⁴⁴ It is expected that use in the afternoon only will be sufficient to achieve the effect. On the other hand, the peripheral contrast-lowering lens that has shown good tolerance and absence of visual field alteration will be used all day long by the subjects under treatment.

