All the data of affiliation, contact telephone number, date of birth, refraction under cycloplegia, axillary length and questionnaire will be entered in a centralized digital history by NOVAR developers. These data will be kept confidential. During follow-up visits, accredited professionals throughout the country will have access to upload the data required for each visit. One month after the eyeglasses are delivered, the professional will conduct a telephone survey to parents to evaluate adherence. The first stage of the study will be completed after one year and the child will be able to continue with the treatment for myopia control according to the consensus guidelines on myopia treatment of the Myopia Study Group of the SAOI (Annex I). For virtual control group, data will be taken from 114 children followed with cycloplegia by the pandemic study group during the years 2018-2019 that showed for an average age of 12 years an annual pre-pandemic progression of -0.45 D. In the present study, We expect to evaluate the progression with peripheral defocus treatment over one year of an equivalent group of children.

WORK PLANNING / GANTT CHART:

Activity	TIME IN MONTHS						
	1	2-4	5-24	25	26	27	28
Project Design	X	X					
Bibliographic search	X			X	X		
Ethics Committee Presentation		X					
Data collection			X				
Data analysis				X	X		
Preliminary results					X	X	
Final Results						X	X
Report writing							X

INCLUSION / EXCLUSION CRITERIA

All consecutive patients of both genders who freely opt for lenses of national industry will be included in the present study. All patients who present any systemic or ocular pathology that may affect their refraction measurements or their evolution will be excluded from the study. Also excluded from the protocol in the follow-up will be those patients who, even using defocus glasses, had in 6 months an improvement equal to that expected without any intervention. These patients will be treated with other options available in our environment at the time of the change. The computerized medical records system will be configured to detect such patients at the time of loading the follow-up data and will send an alert to the investigators.

EVALUATION OF TOLERANCE AND ADHERENCE

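### Treated children can be excluded on their own six-month progression and the plan does not say how they are analysed; comparing only those who remain would favour the lens

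*Combined protocol and SAP*

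**What the plan says.** The section Inclusion / exclusion criteria contains this rule: "excluded from the protocol in the follow-up will be those patients who, even using defocus glasses, had in 6 months an improvement equal"; the benchmark is the course of an untreated child. It adds: "These patients will be treated with other options available in our environment at the time of the change". The records system is to detect such children when follow-up data are entered and to alert the investigators.

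Other sections word this differently:

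- Current state of research makes removal discretionary: "each child who does not respond well with arrest of progression at six months may be removed from the protocol". It also names the size of change at issue, to "progress -0.25 diopters in six months (the resolution limit of the measurement method".
- Human resources sets an alert for progression above 0.25 D in six months, followed by unspecified precautions.
- Exclusion and elimination criteria, at the end, lists no progression criterion.

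On the comparison, Purpose intends to "compare the progression during one year with the national lenses" against foreign lenses and/or an untreated virtual control group. That group is 114 children whose "progression was from 0.43+/-0.52 diopters in one year". No six-month removal rule is described for them. Plan for analysing the results offers Student's t-test or the Mann-Whitney test for numerical variables. It gives no analysis set, no missing-data rule and no rule for children who switch treatment. Efficacy is the secondary objective, but the sample size rests on it: "Statistical calculation for a difference of 0.25 diopters in progression with respect to controls".

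**The concern.** The six-month change is the first half of the one-year outcome. A rule that takes out children who did badly in the first half, applied to one side of the comparison only, lowers mean progression in those who are left even if the lens does nothing. Neither planned test corrects for this, because both take the children presented to them as the group of interest.

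The plan does not say that removed children are left out of the analysis. But a child switched at six months has no one-year value on the national lens, so leaving that child out is what an analyst would most likely do by default.

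The efficacy conclusion is at stake. There is a side effect on the primary objective. Adherence failure is counted as not completing the three visits, so a child removed by the investigators who has no third study visit would be scored as non-adherent.

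**Working it through.** **The plan's own figure.** With a 0.25 D difference, SD 0.50 D, two-sided 0.05 and 80% power (the power is assumed; none is stated), the one-sample formula gives n = ((1.96 + 0.84) × 0.50 / 0.25)² ≈ 31.4, and 31 × 1.2 = 37.2. This matches the stated 31 and 38. So 0.25 D is the yardstick for any bias.

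**Inputs from the documents.** Untreated annual change 0.43 ± 0.52 D (Current state of research); alert above 0.25 D in six months (Human resources); 50 treated children and 20% loss (Sample and sample size), so 40 evaluable; 114 controls.

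**Assumptions not in the documents.** The lens has no effect. The year is two half-years with equal normal distributions (mean 0.215 D each) and correlation ρ from -0.5 (pure measurement noise) to 0.5. Only remaining children are analysed. The 0.25 D alert is taken as the working form of the exclusion rule.

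**Formula.** Half-year SD: s = 0.52 / √(2(1+ρ)). Let c be the cut-off, a = (c - 0.215)/s, f = 1 - Φ(a) the share flagged, and q the share of flagged children removed at random. Then

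false benefit = q · s(1+ρ) · φ(a) / (1 - q·f).

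**Worked case, ρ = 0, c = 0.25, all removed.** s = 0.52/√2 = 0.368; a = 0.035/0.368 = 0.095; φ(a) = 0.397; f = 0.462. False benefit = 0.368 × 0.397 / 0.538 = 0.271 D. With q = 0.5: 0.5 × 0.368 × 0.397 / 0.769 = 0.095 D. With q = 0.25: 0.25 × 0.368 × 0.397 / 0.885 = 0.041 D.

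**Rounding.** Methods defines "spherical equivalent (sphere + 50% of the cylinder"), so with 0.25 D readings the spherical equivalent can move in 0.125 D steps. A strict trigger above 0.25 D then acts at c = 0.3125, or at c = 0.375 if changes move in 0.25 D steps.

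False benefit in D, with all children above 0.25 D removed:

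| ρ | unrounded (c = 0.25) | 0.125 D steps (c = 0.3125) | 0.25 D steps (c = 0.375) |
|---|---|---|---|
| -0.5 | 0.196 | 0.177 | 0.159 |
| 0 | 0.271 | 0.234 | 0.200 |
| 0.5 | 0.327 | 0.272 | 0.222 |

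**Summary over the grid.**

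- All removed: 30–47% of children go, and the false benefit is 0.16–0.33 D.
- Random half removed: 0.06–0.12 D.
- Random quarter removed: 0.03–0.05 D.
- If the exclusion rule is read as half the expected annual change (0.43/2 = 0.215 D, unrounded): 50% removed, 0.21–0.36 D.

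**Chance of a significant false benefit** (40 enrolled and evaluable before removal, against 114; t-test; 20,000 simulated trials per setting): 2.3–2.6% with no removal and 27–84% with all above 0.25 D removed. It is 4.5–7.5% for a random quarter and 8–20% for a random half; these two ranges also cover a trigger at exactly 0.25 D.

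**If the lens works as planned** (0.43 - 0.25 = 0.18 D a year), removing all above 0.25 D takes out 17–38% and adds 0.13–0.22 D to the true 0.25 D.

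**Skewed changes.** With right-skewed half-year changes (gamma shape 1.7, same mean, annual SD about 0.52 D, ρ about 0.5, unrounded, all removed), the false benefit is 0.26 D instead of 0.33 D.

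**Adherence.** If 10 of 50 are lost and no removed child has a third visit, reported failure rises from 20% to (10 + 0.30 × 40)/50 = 44% or (10 + 0.47 × 40)/50 ≈ 58% under full removal.

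**The case against.** The strongest reply is that the plan never says removed children are dropped. One section makes removal optional, the alert leads only to precautions, and the closing elimination list omits progression. The six-month refraction is on the case report form, so removed children do have outcome data. This stands as far as it goes: every bias figure above is conditional on a remaining-children analysis, and the quarter and half scenarios allow for discretion. But the exclusion section itself is not worded as optional, and discretion makes the size of the bias unknown without removing it.

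A reader might infer more than the documents support, in four ways.

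- **That the controls were free of such selection.** The documents only describe no such rule. How the 114 were retained lies in a cited study that is not available here.
- **That the false benefit could reach 0.45 D.** That needs mandatory removal, a reading of exactly 0.25 D counting, changes in 0.25 D steps and ρ = 0.5, all at once. It exceeds the whole expected progression of 0.43 D, so remaining untreated-like children would on average become less myopic by 0.02 D. With 0.125 D steps the same case gives 0.386 D, and the alert says more than 0.25 D.
- **That the sizes are firm.** They rest on normal changes; the upper end falls if changes are right-skewed.
- **That the primary adherence figure will be distorted to 44–58%.** This assumes that no removed child has a third visit and that the 20% loss is additional to removals. The three yearly visits are routine care, and any such error would count against the lens.

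Rescue treatment for a progressing child is clinically proper and is not in dispute.

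**Conclusion.** The concern holds in conditional form. The protocol states a rule that excludes treated children on the first half of their own outcome, and the analysis plan is silent on what happens to them. Combined with a one-year on-lens comparison and an unadjusted two-group test, this biases efficacy toward benefit. The direction is clear if only remaining children are compared. The size depends on the share removed, which the documents do not give: it is small if few are removed and comparable to the planned 0.25 D if the rule is applied to all. The plan is not shown to prescribe that analysis; the likely reading is simply left open. Because efficacy is the secondary objective and the remedy is cheap, this should be fixed but does not undermine the tolerance objective.

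**What to change.** Keep the clinical rescue rule, and reword Inclusion / exclusion criteria so that affected children stop the study lens, may switch treatment, and stay in follow-up and in the efficacy set. Then:

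1. Report one-year change for every child who received the glasses, using the routine 12-month refraction whatever the treatment by then. State that this estimates lens plus rescue.
2. Report with it the six-month change in all children, which removal at that visit cannot select.
3. As a supporting on-lens estimate, fit a repeated-measures likelihood model to all six- and twelve-month values, with values after a switch set to missing. State that under full removal it extrapolates above the cut-off, which on-lens data cannot test. If the slope there differs by ±0.3, the estimate is off by about 0.04 D.
4. Count children removed for progression as treatment failures, separately from adherence failures.
5. State one trigger: above, or at or above, 0.25 D; which eye; and whether removal is mandatory.

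**Cost.** No new visits or patients: the six-month refraction is already on the form and the third visit is routine care. The wording change is needed so that 12-month data on switched children can be collected. The efficacy estimate will be less favourable than a remaining-children mean. With 40 children, the supporting model's standard error is about 0.10–0.18 D if all above 0.25 D are removed, 0.09–0.10 D if half are and 0.08–0.09 D if a quarter are, against 0.52/√40 = 0.08 D with complete data.

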Adherence will be evaluated at the one-year follow-up and will be reported as the number of cases that failed to complete the three scheduled visits in one year with respect to the total number of cases that were enrolled in compliance with the first visit and the delivery of the spectacle. Tolerance of these glasses will be assessed with a tolerance questionnaire that is presented in the attached medical record. This questionnaire has already been tested on 24 subjects aged 18 to 24 years in a pilot trial presented at the International Myopia Conference, as explained in the previous section on the defocus spectacle, showing good tolerance in these subjects. Some tests in younger children that were performed in the last months show that tolerance is very good in them, since minors have greater plasticity and adaptability than young adults previously tested. Tolerance and adherence will be classified as GOOD / BAD, in a dichotomous way, with the cut-off according to the answer given by whether the child tolerated them well or not. On the other hand, tolerance will also be evaluated in dichotomous form with responses to reading and walking

performance.

PROCEDURES TO GUARANTEE ETHICAL ASPECTS

The anonymity of all participants will be preserved. Patients' names will be removed from the database for statistical analysis. The only ones who will know the names of the patients are the physicians involved in their primary care, and they will have to keep the information in their respective institutional medical records and enter the data necessary for the research in a web form designed by the sponsoring company.

The Declaration of Helsinki and its modifications, the Good Clinical Practices guide, the harmonization norms and the resolution of the Ministry of Health 1480/11 will be observed and taken into account as guidelines (See informed consent ANNEX VI). It is stated for the record that the principal investigator does not have any type of conflict of interest since the patenting of the defocus glasses is the responsibility of the sponsor's company.

SAFETY PRECAUTIONS

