It is considered necessary for the development of the study the free coverage by the sponsors (NOVAR) of the peripheral defocus glasses. Money will also be spent for the web form system programmers and for the two ophthalmologists in charge of the study.

The expenses of the medical consultations made by the subjects at the time of enrollment and follow-up will be paid by the medical system of each of the accredited institutions (whether these are social security or prepaid health insurance of the subjects) since no more consultations are required for the study than the three per year recommended for myopia control according to the last consensus of the Myopia Study Group of the SAOI (Annexed). No corneal or eyeball complications are expected (as with contact lenses or drops) since the glasses are a prosthesis that is not introduced into the body and acts at a distance.

CENTERS OF ATTENTION

Eight enrollment centers will be chosen. To avoid biases in the methodology and to adjust the feasibility of developing a joint protocol, training interviews will be conducted with the investigators from each center in a timely manner. The principal investigator will maintain weekly communication by telephone with each of the investigators involved in each center.

ENROLLMENT

Consecutive patients attending the above-mentioned care centres for glasses prescription will be enrolled. Family members will be informed in writing and verbally of the objectives of the study and will sign an informed consent for the study.

Subjects must be willing to participate in a study lasting 1(one) year (it will be explained to them at the beginning of the study that the free treatment materials will in principle only extend for that period).

Risks, discomforts or ethical issues related to participation:

Clinical and biometric ophthalmological studies with or without cycloplegia are routine and free of discomfort for patients.

CRITERIA FOR INCLUSION

- Patients of both sexes aged between 8 and 16 years, without ocular pathology added to myopia.

- Myopia ranges between 2.00 D and 5.00 D in both eyes.
- Refractive astigmatism less than one diopter in each eye.
- Visual acuity 20/25 or better in both eyes.

EXCLUSION AND ELIMINATION CRITERIA

Patients who do not meet the aforementioned inclusion criteria.

Patients with poor adherence to treatment demonstrated by poor compliance with follow-up interviews.

Patients whose family members do not sign the informed consent form.

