Do you take tutoring outside of school? (Circle) YES NO

How many hours do you spend outdoors when you leave school?Hs

How many hours per day do you spend reading books or doing homework?
.....Hs

How much time per day do you spend playing with your cell phone or tablet?
.....Hs

ON ANY SATURDAY OR SUNDAY.....

How many hours per day do you spend reading books or doing homework?Hs

How many hours per day do you spend outdoors on a weekend day?Hs

How much time per day do you spend playing with your cell phone or tablet?
.....Hs

PART II EYEGLASS DELIVERY

DATE

PART II. BIS (ATTACHMENT QUESTIONNAIRE)
AT THE MONTH OF DEFOCUS EYEWEAR DELIVERY (TELEPHONE SURVEY)
DATE

Have you worn the glasses at home during this month? YES NO

Have you worn glasses all day this month? YES NO

If you answered "YES" to any of the above, continue with these

In general, do you tolerate them well? YES NO

Have you ever had trouble turning your head to look sideways? YES NO

Out of the seven days of the week, how many days do you not use them?.....

Have you ever had trouble turning your head to look down when reading? YES NO

Have you ever had trouble turning your head to look down when walking? YES NO

PART III

DATE SECOND VISIT AFTER SIX MONTHS.....

EYE DER SPHERICALCILINDRICAL AXIS.....

SPHERIC IZQ EYE.....CILINDRITRIC AXIS.....

AXIAL LENGTH OD..... OI.....

PART III (BIS) SIX MONTH ADHERENCE QUESTIONNAIRE

Have you worn your glasses at home during this month? YES NO

Have you worn glasses all day during this month? YES NO

If you answered "YES" to any of the above continue with these.....

In general, do you tolerate them well?

YES NO

Have you found it difficult to turn your head to look sideways? YES NO

Of the seven days of the week, how many days do you not use them?

Did you have trouble turning your head to look down when reading? YES NO

Have you had trouble turning your head to look down when walking? YES NO

PART IV

DATE THIRD VISIT AT TWELVE MONTHS.....

RIGHT EYE SPHERICALCILINDRICAL AXIS.....

LEFT EYE SPHERICAL.....CYLINDRICALAXIS.....

AXIAL LENGTH OD..... OI.....

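### The primary adherence result counts attendance at routine visits, not daily wear, and the wear answers collected on the study forms feed no adherence result

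*Combined protocol and SAP*

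**What the plan says.** OBJECTIVES (Primary) asks whether the glasses are "well tolerated and adhered to with daily use in childhood and adolescence".

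EVALUATION OF TOLERANCE AND ADHERENCE turns this into a result. Adherence is evaluated at one year and "reported as the number of cases that failed to complete the three scheduled visits in one year". The plan also fixes the denominator: the count is taken "with respect to the total number of cases that were enrolled in compliance with the first visit and the delivery of the spectacle". Later in the same section: "Tolerance and adherence will be classified as GOOD / BAD, in a dichotomous way, with the cut-off according to the answer given", where the answer meant is whether the child tolerated the glasses well.

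On the visits, FINANCIAL RESOURCES explains that they are paid for as ordinary care, "since no more consultations are required for the study than the three per year recommended for myopia control". The record forms place the visits after the first at "DATE SECOND VISIT AFTER SIX MONTHS" (PART III) and "DATE THIRD VISIT AT TWELVE MONTHS" (PART IV).

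On wear, the one-month telephone form (PART II BIS) and the month-6 form (PART III BIS, titled "SIX MONTH ADHERENCE QUESTIONNAIRE") each ask whether the glasses were worn at home that month, whether they were worn all day, and on how many days of the week they were not used. The tolerance question and the days-not-used question follow only after a YES to one of the first two. METHODS and SAFETY PRECAUTIONS both say the one-month survey serves to evaluate or verify adherence. PLAN FOR ANALYSING THE RESULTS gives general rules for summarising variables and names no wear item or cut-off.

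**The concern.** The objective is about use of the glasses, whereas the reported figure is about turning up. The visits are ones the child is advised to make anyway for myopia control, so stopping the glasses removes no reason to attend. Attendance is therefore a weak proxy for wear here.

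The second use of the word adherence, graded by the tolerance answer, does not measure daily use either. It can also give a different label from the visit count for the same child.

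What is at stake is the primary conclusion. The study could report good adherence when few children wear the glasses, or poor adherence when children who wear them daily miss a visit. Leaving two meanings in place also leaves room to choose between them after the data are seen.

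**Working it through.** The documents give no target, expected rate or power for adherence, so there is no stated figure to reproduce. The check compares the definitions and then illustrates the size.

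**Step 1: what the visit count can detect.** The first visit is a condition for entering the denominator. Only two attendances, at months 6 and 12, can vary. No wear answer enters the count.

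**Step 2: four children under the plan's two uses of the word.**

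| Child | Visit count | Good/bad label |
|---|---|---|
| Attends all visits, answers NO to both wear items | Adherent | No value (tolerance not asked) |
| Wears daily, tolerates well, misses the month-12 visit | Not adherent | Good |
| Wears, attends all visits, answers NO on tolerance | Adherent | Bad |
| Attends all visits, tolerates well, six unused days a week | Adherent | Good |

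The last row shows that even both labels together do not identify daily use. The first row shows that a child who has stopped is missing from the tolerance result at that survey rather than counted as bad.

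**Step 3: size.** Inputs from SAMPLE AND SAMPLE SIZE: N = 50 and a 20% loss to follow-up (an allowance made for the progression comparison and borrowed here). The non-wear rates are assumptions, because the documents give none.

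- Failures on the visit count: 0.20 × 50 = 10, so 10/50 = 20.0% (exact 95% CI 10.0 to 33.7).
- Attenders: 50 − 10 = 40, so 40/50 = 80.0% (66.3 to 90.0).
- If k attenders do not wear the glasses, the share who attend and wear is (40 − k)/50:
  - k = 0 (0% of 40): 40/50 = 80%
  - k = 4 (10%): 36/50 = 72%
  - k = 8 (20%): 32/50 = 64%
  - k = 12 (30%): 28/50 = 56% (41.3 to 70.0)
- k does not appear in the visit count, which stays at 20% failures in every line.

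Wear among the 10 non-attenders is also unknown. If all of them wore the glasses, they would add 10/50 = 20 percentage points to each share of wearers.

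**Step 4: efficacy removals.** INCLUSION / EXCLUSION CRITERIA takes out children at six months for lack of response even though they use the glasses. Read literally, such a child who then has no third visit is an adherence failure. Each one not already among the 10 adds 1/50 = 2 percentage points.

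**The case against.** Several points on the other side are fair.

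- **The plan does collect wear, for an adherence purpose.** This stands. A reader might infer that wear is ignored altogether, but the documents do not support that. The wear items decide who is asked about tolerance, and the general analysis rules would allow them to be tabulated. What is missing is a cut-off and an adherence result derived from them.
- **The two rules need not contradict each other.** One is a one-year visit measure, and the other may be a loosely translated way of splitting survey answers. Two measures taken at different times can differ for one child. That also stands: the defect is one label with two meanings. A count of children classed differently would need tolerance rates that the documents do not give, and an answer from every child, which the skip in the form prevents.
- **The pilot might seem to give a non-wear rate.** DEFOCUS GLASSES OF NATIONAL DESIGN reports good reading tolerance in 70% of 17 respondents. This is tolerance, not wear. The evaluation section describes a pilot of 24 subjects aged 18 to 24, so even the source is unclear. It cannot anchor the 30% used above.
- **The month-6 form might seem to cover the first half-year.** It does not. Both surveys ask about the current month only.
- **The 12-month form shows no questionnaire.** A reader might infer that none was planned, but the form text may be cut.
- **There is no formal primary endpoint, hypothesis test or power for adherence.** True. But the objective is ranked primary, and this is the section that makes it measurable.

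None of these answers the main point: the figure the plan calls adherence contains no information on wear.

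**Conclusion.** The concern holds and should be corrected before analysis. The stated adherence figure is retention at months 6 and 12. It cannot separate children who wear the glasses from those who do not, although that is the primary objective. The second, tolerance-based use of the word makes the result ambiguous.

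This conclusion rests on the text alone. The size is illustrative: with 50 children, the plan's own 20% loss, and an assumed 0% to 30% of attenders not wearing the glasses, the share who attend and wear moves by 24 percentage points (80% to 56%) while the reported figure does not change. CURRENT STATE OF RESEARCH mentions 100 children instead of 50. The same rates would give the same percentages, with a narrower interval for failures (20/100 = 20.0%, exact 95% CI 12.7 to 29.2).

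The documents do not show that wear will be poor, only that this figure could not reveal it.

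**What to change.** In EVALUATION OF TOLERANCE AND ADHERENCE:

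1. Rename visit completion as retention and report it separately, with the six-month removals for lack of response shown apart.
2. Define adherence from the form items: YES to a wear item and zero days per week not used. This follows the daily use in the primary objective and the every-day instruction in METHODS. Count NO to both wear items as not adherent, and show the full distribution of days not used.
3. Apply the good/bad grading to tolerance only.
4. Keep the denominator of all children given glasses. State that removals under INCLUSION / EXCLUSION CRITERIA and under EXCLUSION AND ELIMINATION CRITERIA stay in it. For children not reached or not asked, give best-case and worst-case bounds, with exact 95% CIs.
5. Report months 1 and 6 separately, and state that each answer covers about one month and that the other months are unmeasured. Because the plan evaluates adherence at one year, give the same short questionnaire at the existing 12-month visit if it is not already there. Name the main time point before analysis.
6. USE OF GLASSES tells the child to wear the glasses as much as they can, while METHODS limits the defocus glasses to the late afternoon and evening of every day. The sponsor must reconcile these. Until then, report the all-day item separately.

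Cost: wording before analysis. Months 1 and 6 need no new data, and a 12-month questionnaire adds a few questions at an existing visit. The downside is that reported adherence may be lower and less precise, and that wear remains self- or parent-reported.
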